6.6.1.5. Guidelines for the Management of Eye Toxicity Associated With **Vision Changes**

If subject experiences an event of confirmed new retinal abnormality (such as retinal detachment, vitreous detachment, retinal edema, retinopathy, chorioretinopathy, detachment of retinal pigment epithelium, and detachment of macular retinal pigment epithelium) during study treatment, it must be reported as an adverse event or a serious adverse event if Grade 3 or higher. Any new and clinically significant symptoms, such as but not limited to, blurred vision, partial or complete loss of vision, double vision, floaters or color spots or halos around light, change in color or night vision, photophobia, ocular pain or stinging sensation, or foreign body sensation should be further evaluated and managed per the guidelines in Table 15.

Amsler Grid (illustrated in Section 10.9): For any positive Amsler grid test, the subject should be referred for a full ophthalmologic examination within 7 days. However, if the subject has an abnormal Amsler grid test and otherwise normal ophthalmologic exam at baseline (during Screening), a repeat ophthalmologic examination would be recommended only if, in the opinion of the investigator, there is a likelihood of significant change from the subject's baseline Amsler grid test at Screening, or the subject has developed new clinical symptoms.

Table 15: Guidelines for Management of Eye Toxicity				
Grade and Definition	Study Drug (Erdafitinib) Management	Symptom Management		
Grade 1: Asymptomatic or mild symptoms; clinical or diagnostic observations only	Refer for an ophthalmologic examination. If an ophthalmologic exam cannot be performed within 7 days, withhold treatment with erdafitinib until an examination can be performed.	Refer the subject for an ophthalmologic examination. For retinal pathology		
Or abnormal Amsler grid test	If there is no evidence of eye toxicity on ophthalmologic examination, continue erdafitinib at the same dose level. If diagnosis from ophthalmologic examination is keratitis or retinal abnormality such as central serous retinopathy (CSR)/ retinal pigment epithelial detachments (RPED), withhold erdafitinib until signs and symptoms have resolved. If toxicity is reversible (complete resolution or stabilization and asymptomatic) in 4 weeks according to ophthalmologic examination, resume erdafitinib at the next lower dose level after consultation with the sponsor's medical monitor. Retinal pigment epithelial detachment, if observed, should be monitored at approximately 2-3-week intervals until resolution. Monitor for recurrence every 1 to 2 weeks for a month and as clinically appropriate thereafter. If there is no recurrence, then re-escalation can be considered in consultation with the medical monitor.	perform OCT as appropriate and consider referral to a retinal specialist for further evaluation. Follow specific treatment per the ophthalmologist's recommendation.		
Grade 2: Moderate; minimal, local, or noninvasive intervention indicated; limiting age-appropriate instrumental ADL Visual acuity 20/40 or better or \leq 3 lines of decreased vision from baseline	Immediately withhold erdafitinib. If there is no evidence of drug-related corneal or retinal pathology on ophthalmologic examination, withhold erdafitinib until signs and symptoms have resolved. Resume erdafitinib therapy at the next lower dose level. If diagnosis from ophthalmologic examination is keratitis or retinal abnormality such as CSR/RPED, withhold erdafitinib until signs and symptoms have resolved, stabilized, or subject is lost to follow-up or withdraws consent (which ever happens first). If toxicity is reversible (complete resolution or stabilization and asymptomatic) within 4 weeks according to ophthalmologic examination, resume erdafitinib at the next lower dose level after consultation with the sponsor's medical monitor. Retinal pigment epithelial detachment, if observed, should be monitored at approximately 2-3-week intervals until resolution. Monitor for recurrence every 1 to 2 weeks for a month and as clinically appropriate thereafter. If there is no recurrence, then re-escalation can be considered in consultation with the medical monitor.	Refer subject to an ophthalmologist for evaluation with an ophthalmologic examination. For retinal pathology, perform OCT as appropriate and consider referral to a retinal specialist for further evaluation. Follow specific treatment per the ophthalmologist's recommendation.		

 Table 15:
 Guidelines for Management of Eye Toxicity

Table 15. Guidennes for Management of Eye Toxicity			
Grade and Definition	Study Drug (Erdafitinib) Management	Symptom Management	
Grade 3: Severe or medically significant but not immediate sight-threatening; hospitalization or prolongation of existing hospitalization indicated; disabling; limiting self-care ADL Visual acuity worse than 20/40 or > 3 lines of decreased vision from baseline	If the toxicity is Grade 3, report as a serious adverse event and withhold erdafitinib. If the toxicity is Grade 3 and reversible (complete resolution or stabilization and asymptomatic) within 4 weeks and the subject is having clinical benefit, and the investigator and the sponsor's medical monitor agree that continuation of treatment is in the best interest of the subject, then erdafitinib may be resumed at 2 dose levels lower if appropriate. Retinal pigment epithelial detachment, if observed, should be monitored at approximately 2-3-week intervals until resolution. Monitor for recurrence using appropriate investigations every 1 to 2 weeks for a month and as clinically appropriate thereafter. For cases of recurrence, consider permanent discontinuation.	Refer subject to an ophthalmologist for evaluation with an ophthalmologic examination. For retinal pathology, perform OCT as appropriate and consider referral to a retinal specialist for further evaluation. Follow specific treatment per the ophthalmologist's recommendation.	
Grade 4: Sight- threatening consequences; urgent intervention indicated; blindness (20/200 or worse) in the affected eye Visual acuity 20/200 or worse in affected eye	Permanently discontinue treatment with erdafitinib. Report as a serious adverse event and monitor resolution of the event until complete resolution, stabilization or the subject is lost to follow-up or withdraws consent (which ever happens first).	Promptly refer subject to an ophthalmologist for evaluation with an ophthalmologic examination. Follow specific treatment per the ophthalmologist's recommendation.	
ADL=Activities of Daily Living, OCT= Optical Coherence Tomography			

Table 15:Guidelines for Management of Eye Toxicity

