8.4.7. Adverse Events of Special Interest

Central serous retinopathy (CSR) is considered an adverse event of special interest. Retinal abnormalities should be reported as adverse events or as serious adverse events if the severity is Grade 3 or higher. Instructions for assessing vision abnormalities during the study are provided in Section 8.3.5.

Growth disorders (including accelerated bone growth and SCFE) and fractures in children and adolescent subjects (≥ 6 to <18 years) is an adverse event of special interest for erdafitinib. Growth disorder-related and fracture-related AEs of Grade 3 or higher severity in children and adolescents, regardless of seriousness, will be reported to the sponsor within 24 hours (see Section 10.4.).

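### In Table 15 the Grade 2 and Grade 3 visual acuity criteria overlap, so one new eye event can fit both grades, which carry different restart and reporting instructions

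*Protocol*

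**What the plan says.** Protocol Table 15 has a column that gives each grade with its definition. The last element of the definition for Grades 2, 3 and 4 is a visual acuity criterion.

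- **Grade 2:** "Visual acuity 20/40 or better or" a loss of at most "3 lines of decreased vision from baseline".
- **Grade 3:** "Visual acuity worse than 20/40 or > 3 lines of decreased vision from baseline".

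The instructions attached to the two grades differ.

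- **Grade 2, no drug-related corneal or retinal pathology:** withhold until signs and symptoms resolve, then "Resume erdafitinib therapy at the next lower dose level".
- **Grade 2, keratitis or a retinal abnormality:** the same step down, if the event is reversible within 4 weeks and after consulting the medical monitor. Re-escalation can be considered if there is no recurrence.
- **Grade 3:** report as a serious adverse event (SAE) and withhold. If the event is reversible within 4 weeks, the subject is benefiting, and the investigator and medical monitor agree, "then erdafitinib may be resumed at 2 dose levels lower if appropriate". "For cases of recurrence, consider permanent discontinuation".

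On reporting, Section 8.4.7 states: "Retinal abnormalities should be reported as adverse events or as serious adverse events if the severity is Grade 3 or higher". Sections 6.6.1.5 and 10.4.3 set the same threshold. Section 10.4.2 assigns the severity of all adverse events by NCI-CTCAE version 5 or higher.

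**The concern.** A grading table that drives dosing and expedited reporting should put each finding in one grade. Here two sites could see the same acuity result, both follow Table 15, and reach different grades. They would then differ in how far the dose steps down, in whether clinical benefit must be judged before restart, in the response to recurrence, and in whether the event is reported as an SAE within 24 hours (Section 8.4.1).

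Two places in the protocol raise the stakes.

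- **Table 6:** for a child up-titrated to 4 mg, the first reduction is 3 mg and the second is to stop. One level or two levels down can therefore decide whether treatment continues.
- **Appendix 13:** in the long-term extension only SAEs are reported. An event called Grade 2 and not otherwise serious would go unreported, while the same event called Grade 3 would be reported.

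**Working it through.** The plan gives no figure to reproduce, so the check is on the wording.

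**Logic.** Let A mean acuity 20/40 or better, and B mean three lines or fewer lost.

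- Grade 2 = A or B.
- Grade 3 = (not A) or (not B).
- Both grades = (A and not B) or (not A and B).

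Both grades are met whenever exactly one of A and B is true. No acuity chart is needed for this result.

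**The two directions.**

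1. *Worse than 20/40, three lines or fewer lost.* A fall from 20/40 to 20/50 is one line: Grade 2 by lines lost, Grade 3 by absolute acuity. A subject who starts at 20/50 and loses one more line in a new eye event is in the same position.
2. *Still 20/40 or better, more than three lines lost.* A fall from 20/16 to 20/40 is four lines on a logMAR-type chart, and 20/15 to 20/40 is four lines on a Snellen-type chart. Each is Grade 2 by absolute acuity and Grade 3 by lines lost.

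**Enumeration.** The documents name no chart, so two were assumed, each running from 20/10 to 20/200. Every baseline-to-worse pair was classified.

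| Assumed chart | Steps | Possible declines | Fit both grades | Direction 2 | Direction 1, baseline 20/40 or better | Direction 1, baseline worse than 20/40 |
|---|---|---|---|---|---|---|
| logMAR-type | 14 | 14 × 13 / 2 = 91 | 27 | 6 | 6 | 15 |
| Snellen-type | 12 | 12 × 11 / 2 = 66 | 21 | 3 | 6 | 12 |

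The rows add up: 6 + 6 + 15 = 27 and 3 + 6 + 12 = 21. No decline falls outside both grades on either chart. Among declines that start at 20/40 or better and end better than 20/200, 12 (logMAR-type) and 9 (Snellen-type) fit both grades. These are counts of combinations on assumed charts, not patient frequencies.

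**Search for a tie-break.** Section 6.6.1.5 and Table 15 give none. Section 10.4.2 has no rule for an event that meets two grades. The amendment history records that Amendment 4 added the acuity values to the grade definitions for clarity, so they are meant to help decide the grade.

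**The case against.** The strongest reply is that Table 15 guides management and does not grade adverse events. For hyperphosphatemia (Table 7) and nail events (Table 12) the protocol says expressly that the table sets the grade. Section 6.6.1.5 says only that symptoms are evaluated and managed by Table 15, while Section 10.4.2 and SAP Section 6.1.2 grade by NCI-CTCAE. This stands in part. A reader might infer that Grade 3 or higher counts of central serous retinopathy, an event of special interest, depend on which limb a site applies. The documents allow that but do not show it, because those summaries use NCI-CTCAE. The reply does not remove the point: Table 15 defines the grades and itself orders SAE reporting at Grade 3.

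A second reply is that acuity is only part of each definition. The descriptors (moderate with limited instrumental activities, against severe with limited self-care) will separate many cases. That is fair, but no text says that they override acuity.

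A third is that practice differs less than the wording suggests. Both grades withhold drug and refer to an ophthalmologist, and for keratitis or retinal events the medical monitor is involved before restart in either grade. This stands too. The step down, the benefit condition, the recurrence instruction and the SAE requirement still differ.

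Three further inferences are tempting and not supported.

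- *A subject with poor baseline acuity is Grade 3 with no change.* Section 6.6.1.5 concerns new abnormalities and symptoms, and Section 10.4.1 requires an event to be new or aggravated from baseline. Stable poor acuity is not an event.
- *Every subject with baseline acuity worse than 20/40 is affected.* Only those who develop a new eye event can be.
- *Grade 3 alone is serious.* Table 15 also makes Grade 4 an SAE, and a Grade 2 event may be serious on the general criteria in Section 10.4.1.

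**Conclusion.** The overlap is real and certain on the text. The Grade 2 and Grade 3 acuity criteria are both met in any new eye event in which absolute acuity and lines lost point different ways. Table 15 then gives two sets of restart and recurrence instructions, with mandatory SAE reporting under one of them, and the documents do not say which applies.

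The size in patients is unknown. Eligibility sets no acuity limit (it excludes current central serous retinopathy or retinal pigment epithelial detachment), acuity is measured at screening, and no distribution is given. Loss of more than three lines while still at 20/40 or better needs a very good baseline, so that direction is probably the rarer one. The conclusion assumes that *or* is read literally in both rows. The primary endpoint, sample size and error control are not touched. This is an inconsistency of wording with a safety consequence, and it should be corrected.

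**What to change.** Reconcile the Grade 2 and Grade 3 acuity definitions in Table 15 so that each combination of absolute acuity and lines lost falls in one grade. State how a baseline already worse than 20/40 is handled when a new eye event occurs. State how Table 15 relates to the NCI-CTCAE grading in Section 10.4.2, and that one grade serves both dose management and the reporting rules in Sections 6.6.1.5, 8.4.7 and 10.4.3. The clinical content is for the sponsor and its ophthalmology advisers; no view is taken here on which limb, cut-off or dosing rule is right.

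The cost is a change of table wording or a protocol clarification. No new assessment is needed, since acuity is already measured at screening and Table 15 already refers eye events for ophthalmologic examination.

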6.6.1.6. Guidelines for the Management of Dry Eye

- General considerations: Avoid unnecessary exposure to sunlight and use sunglasses in bright light.
- **Prophylactic management:** Frequent use of artificial tear substitutes and ocular demulcents is strongly recommended, ie, every 2 hours during awake time.
- Reactive management:
 - Withhold erdafitinib for Grade 3 toxicity
 - Artificial tear substitutes if not started, every 2 hours during awake time
 - Ocular demulcents
 - Severe treatment-related dry eye should be evaluated by an ophthalmologist

6.7. Study Drug After Study Completion

Once the end of data collection timepoint (see Section 5.5) has been achieved, follow-up of subjects will end, and data collection will conclude. Only serious adverse events will be reported in the company safety repository (See Appendix 13). Subjects in the Treatment Phase who are continuing to derive benefit from study treatment as determined by their investigator may continue to receive access to study treatment either on this study, with only data collection of serious adverse events in the company safety repository (see Section 5.5) via LTE phase (see Appendix 13) or a post-trial access program, when permitted by local regulations. Provision may continue until the subject can commercially access study treatment within the local healthcare system, until a decision is made not to pursue the studied indication, until the investigator decides it is in the best interest of the subject that study treatment be discontinued, or until 2 years after local marketing authorization is obtained for the studied indication, whichever comes first.

7. DISCONTINUATION OF STUDY DRUG AND SUBJECT DISCONTINUATION/WITHDRAWAL

A subject will be considered as having completed the study if the subject has died during the study or has not been withdrawn from the study by the end of the study.

7.1. Discontinuation of Study Drug

A subject's study drug must be discontinued if:

- The subject withdraws consent or assent to receive study drug
- The investigator believes that for safety reasons or tolerability reasons (eg, adverse event) it is in the best interest of the subject to discontinue study drug
- The subject becomes pregnant; discontinuation of study treatment in this instance should be discussed with the medical monitor
- Progression of disease is assessed

Exception: if the investigator and medical monitor agree that continuation of treatment is in the best interest of the subject considering the terminal nature of the underlying disease, he/she may receive treatment until such time as the treating physician and the medical monitor agree that further continuation of treatment is no longer beneficial to the subject.

- The subject refuses further treatment with the study drug
- The sponsor terminates the study
- Investigator decision approved by the sponsor

If a subject discontinues study drug for any reason, an End-of-Treatment Visit should be conducted 30 (+7 days) after the subject's last dose of study drug. The primary reason for treatment discontinuation will be clearly documented in the subject's medical record and recorded in the CRF. Study drug assigned to the subject who discontinued study drug may not be assigned to another subject.

7.2. Subject Discontinuation/Withdrawal From the Study

A subject will be withdrawn from the study for any of the following reasons:

- Lost to follow-up
- Withdrawal of consent

When a subject withdraws before study completion, the reason for withdrawal is to be documented in the CRF and in the source document.

A subject (as well as guardian for children and adolescent subjects) declining to return for scheduled visits does not necessarily constitute withdrawal of consent. Alternate follow-up mechanisms that the subject agreed to when signing the consent form apply as local regulations permit.

7.2.1. Withdrawal From the Use of Research Samples

The subject or their legal representative may withdraw consent for use of samples for future research. In such a case, samples will be destroyed after they are no longer needed for the clinical study. Details of the sample retention for research are presented in the ICF.

8. STUDY ASSESSMENTS AND PROCEDURES

Overview

The Schedule of Activities (Section 1.3 for Adults and Section 1.4 for Children and Adolescents) summarizes the frequency and timing of safety, efficacy, PK, biomarker, and other measurements applicable to this study. Patient-reported outcome questionnaires should be completed before any other assessments at each clinic visit.

The number of samples and the blood volume will vary depending on the number of cycles of the study drug that the subject receives. The total blood volume to be collected from each subject will be approximately 230 mL for adults and 275 mL for children and adolescents over 6 cycles (including the screening and end of study visits, approximately 15 mL is collected at each additional cycle). (See Section 4.2.4 for additional information regarding the blood volume). Unscheduled blood samples may be required for safety issues of individual subjects.

Study-Specific Materials

The investigator will be provided with the following supplies:

- Erdafitinib Investigator's Brochure
- Pharmacy manual/study site Investigational Product Manual and the Investigational Product Preparation Instructions
- Laboratory manual
- National Cancer Institute Common Terminology Criteria for Adverse Events (NCI-CTCAE) Version 5 or higher

- PRO completion guidelines
- Imaging Guidelines
- IWRS Manual
- Electronic data capture (eDC) Manual
- eSource Manual
- Sample ICFs

8.1. Study Procedures

8.1.1. Screening Phase

The Screening Phase will consist of a Molecular Eligibility Screening Period and a Full Study Screening Period. The consent process for the Molecular Eligibility Screening Period may occur in 1 of 3 ways:

- If archived tissue is available, the Molecular Eligibility Informed Consent Form (ICF) is signed.
- If a new tissue biopsy is required, the Full-study ICF is signed.
- If a historical report (local testing) is available indicating the subject is molecularly eligible for the study, upon sponsor review and approval, the Molecular Eligibility Screening Period is complete and the subject signs the Full-study ICF, or the Full-study ICF and Molecular Eligibility ICF are combined and signed at the same time.

The Full Study Screening Period starts within 30 days of the first dose of study drug on Cycle 1 Day 1. All subjects who are eligible for the study based on molecular screening must sign the Full-study ICF.

8.1.1.1. Molecular Eligibility Screening Period

Prior to implementation of Amendment 4, central testing for FGFR alterations was performed on subject tissue samples from the tumor histologies listed in Figure 6. Subjects with any solid tumor histology (excluding urothelial cancer) may meet molecular eligibility by submitting a local/historical test result showing an FGFR mutation or fusion. (The World Health Organization [WHO] Classification of Tumours will be used to categorize tumor histologies in this study.) Consent for molecular eligibility screening (but not full study screening) may be performed remotely including consent by telephone or video consultation, unless not permitted according to local guidance.

During the Molecular Eligibility Screening Period, originally the protocol allowed for 2 approaches to determine eligibility for this study, ie, central or local molecular screening: (Starting with Amendment 4, central molecular testing will no longer be used for all subjects.)

Local/historical report with evidence of an FGFR mutation or fusion in any solid tumor histology (except urothelial cancer)

Results of locally performed or commercial testing from tissue or blood (NGS tests, digital counting methods, or the Qiagen therascreen FGFR RT-PCR test) performed by a CLIA-certified or regional equivalent laboratory may be used to meet molecular eligibility.

If a subject is enrolled based on local testing, a tissue sample must be submitted for: retrospective confirmation of FGFR^a status (where applicable); diagnostic development; biomarker research.

	Central Molecular Screening Note: Starting with Amendment 4, only local reports will be used for molecular screening.	OR	Local Result
Eligible Tumor Types ^a	 Pediatric subjects with any solid tumor High-grade glioma (glioblastoma) Low-grade gliomas Squamous cell head and neck cancers Soft tissue sarcoma Cholangiocarcinoma Endometrial, cervical, and ovarian cancers Squamous non-small cell lung cancer (NSCLC) Renal cell cancer Esophageal cancer Gastric cancer Breast cancer^b Hepatocellular carcinoma Pancreatic cancer Salivary gland tumors Colorectal cancer Thymic cancer/thymoma 		Any solid tumor (except urothelial cancer) with an eligible FGFR mutation or fusion
Applicability	Subjects without available local FGFR testing results		Subjects with local FGFR testing results

Figure 6:	Molecular Screening Approaches
-----------	--------------------------------

Note: Biopsy of the brain, lung/mediastinum, pancreas, or for endoscopic procedures extending beyond the esophagus, stomach, or bowel is not permitted; please contact sponsor prior to conducting biopsy.

FGFR=fibroblast growth factor receptor

^a For enrollment in each tumor histology, the sample size is capped at approximately 30 subjects. The tumor histology list for this cap, including a group of Other, is pre-defined in Table 16.

^b Limited to women with hormone-sensitive, ie, estrogen receptor (ER)/progesterone receptor (PR) positive, breast cancer.

If a subject meets the molecular eligibility criteria, the subject may continue study screening under the Full-study ICF for determination of full-study eligibility.

^a The results of retrospective central confirmation do not affect the subject's eligibility for the study. Testing results of retrospective confirmation studies will not be communicated to the site.

